Figure 9: PAP-derived epitope-specific cellular immune responses can be detected long-term after initial immunization. Peripheral blood mononuclear cells were obtained from an HLA-A2-expressing patient at multiple intervals following an initial 6 biweekly immunization series and 6 monthly booster immunizations 18 months later (red bars indicate timing of these immunizations). Cells were stimulated *in vitro* for 1 week with peptides and assayed for the frequency of epitope-specific T cells among CD3+CD8+ cells by HLA-A2-specific PAP peptide-specific pentamers (ProImmune, Inc.).

5. **Objectives**

A. **Primary Objectives**

1. To evaluate the 2-year metastasis-free survival of patients with non-metastatic prostate cancer (clinical stage D0) treated with a DNA vaccine encoding PAP, with GM-CSF as an adjuvant, versus patients treated with GM-CSF only.

B. **Secondary Objectives:**

1. To evaluate if immunization with a DNA vaccine encoding PAP prolongs PSA doubling time in patients with non-metastatic prostate cancer
2. To evaluate the safety and tolerability of the pTVG-HP DNA vaccine administered to patients with clinical stage D0 prostate cancer
3. To evaluate the median progression-free survival, and PSA progression-free survival, of patients with non-metastatic prostate cancer (clinical stage D0) treated with a DNA vaccine encoding PAP, with GM-CSF as an adjuvant, versus patients treated with GM-CSF only.

C. **Laboratory Objectives:**

1. To determine if immunization with a DNA vaccine encoding PAP elicits antigen-specific T-cell and/or IgG responses
2. To determine if immune monitoring of T-cell responses can be accurately and reproducibly conducted in a multi-center vaccine trial
3. To determine if the development of PAP-specific T-cell immune responses are associated with clinical responses.

D. **Exploratory Biomarker Objectives – Expanded Subject Cohort:**

1. To determine if baseline immune responses specific for PAP are predictive (or not) for the development of PAP-specific T-cells and/or are associated with 2-year metastasis-free survival in the cohort of patients who receive a DNA vaccine encoding PAP
2. To determine if antigen spread (the development of immune responses to other cancer-associated proteins) is associated with 2-year metastasis-free survival
3. To determine if Quantitative Total Bone Imaging (QTBI) by NaF PET/CT can identify bone lesions in this patient population not detected by standard bone scintigraphy

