High-throughput immunoblot (HTI): An exploratory objective of the study will be to determine if patients treated develop “off-target” prostate cancer antigen-specific immune responses as evidence of antigen spread. Future studies may evaluate T-cell responses to non-targeted antigens. However, the primary evaluation will be to evaluate IgG responses to a panel of prostate-associated antigens as we have previously reported in patients treated with vaccines or other immune-modulating agents [65, 66, 67]. IgG specific for 126 antigens, including 29 cancer-testis antigens [68, 69] and 97 prostate antigens frequently immunologically recognized [70, 71, 72, 73] will be identified by screening a high-density phage array expressing these individual antigens, as we have previously reported [65, 67, 68]. An alternative to this approach may include the evaluation of responses to panels of protein antigens fixed to support membranes provided by commercial vendors. The primary analysis will be conducted using sera obtained at 6 months, and compared with IgG responses identified at baseline, to determine whether IgG specific for individual antigens are elicited over time. Other time points will be assessed to determine the durability and kinetics of immune response development, and confirmatory ELISA studies will be performed where feasible.

REPORTING AND RESPONSE DEFINITION: A positive IgG response will be defined as an immunoreactive spot to a defined antigen, scored by at least 3 of 4 independent reviewers, and detectable to at least 2 of 3 replicates per immunoblot membrane, or by statistically defined criteria using commercial antigen sources. An IgG response resulting from immunization will be defined as an immunoreactive antigen identified at the 6-month (or other post-treatment time for subsequent analyses) time point that was not identified at the pre-treatment time point.

C. Serum PSA Doubling Time Response

See Section 13 for further details. Serum PSA doubling-time response will be considered a secondary endpoint. The pre-treatment serum PSA doubling time will be calculated from all serum PSA values available from the same clinical laboratory using the same assay for the three-six month period prior to study treatment, not on other treatments for prostate cancer, up to and including the PSA value obtained at screening, using the Memorial Sloan-Kettering Cancer Center

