The detection of antigen spread to other prostate associated antigens, and the identification of specific antigens recognized, will be analyzed descriptively. In addition, logistic regression analysis will be conducted to evaluate whether antigen spread is associated with the generation of PAP-specific immune responses elicited as a result of treatment. The dependent variables will be the detection of IgG responses to ≥ 1 “off-target” antigen at 6 months (and not present pre-treatment) while treatment arm and 6-month PAP-specific immune responses (no vs. yes) will be included as covariates. The results will be reported in terms of odds ratios and the corresponding 95% confidence intervals.

Results from the QTBI analysis will be used to determine whether individuals with identifiable bone lesions exhibit early disease progression (within 1 year) by standard bone scintigraphy and/or CT scans, and whether the time to metastatic disease is different with respect to treatment group. Specifically, the association between baseline QTBI parameters and time to disease progression will be evaluated using Cox proportional hazard analysis. Analogously, logistic regression analysis will be conducted to evaluate presence of lesions detected by NaF PET/CT at baseline is associated with early disease progression (within 1 year) rate.

Furthermore, % changes in QTBI parameters from the baseline to the 3 and 6 months assessment will be calculated and summarized in terms of means, standard deviations, medians and ranges, stratified by treatment arm. A linear mixed effects model with subject specific a random effects will be used to evaluate the association between changes in QTBI parameters and changes in PSA doubling time.

Due to the exploratory nature of the biomarker evaluations proposed in this trial, no adjustments will be made for multiple comparisons. Except for the primary endpoint which will be compared

at the one-sided 5% significance level, all other comparisons will be made using a two-sided test at a significance level 0.05 without adjustment for multiplicity. Data analysis will be conducted using SAS software (SAS Institute, Carey NC), version 9.3 or greater.

14. Administrative Considerations

A. Specimen Handling

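### No planned analysis links antigen spread to metastasis-free survival, which is the question exploratory objective 2 asks

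*Combined protocol and SAP*

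**What the plan says.** Section 5.D, objective 2 (also in the Synopsis) reads: "To determine if antigen spread (the development of immune responses to other cancer-associated proteins) is associated with 2-year metastasis-free survival". Section 2.E repeats the general aim of finding immune measures, at baseline or after treatment, that predict two-year MFS. It names no method.

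Section 11.B.5 describes the assay. The panel covers "IgG specific for 126 antigens, including 29 cancer-testis antigens [68, 69] and 97 prostate antigens frequently immunologically recognized". A positive call must be "scored by at least 3 of 4 independent reviewers, and detectable to at least 2 of 3 replicates per immunoblot membrane". If a commercial panel replaces the phage array, the alternative is given only as "or by statistically defined criteria using commercial antigen sources". A treatment-induced response is an antigen seen at the 6-month "time point that was not identified at the pre-treatment time point". The section adds that "confirmatory ELISA studies will be performed where feasible".

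Section 13, Statistical Analysis Plan, Biomarker endpoints, then gives two analyses of spread: a descriptive summary, and a logistic regression to evaluate "whether antigen spread is associated with the generation of PAP-specific immune responses elicited as a result of treatment". The dependent variable is IgG to one or more off-target antigens at 6 months that was absent before treatment. The covariates are treatment arm and 6-month PAP response (yes or no).

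**The concern.** The objective treats antigen spread as a possible marker of clinical outcome. The model treats it as a result of treatment and PAP response, and MFS does not appear in it. If Section 13 is followed as written, the trial will report whether spread accompanies PAP immunity and will say nothing formal about objective 2.

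If the analysis is left to be devised after unblinding, its method, cut-off and handling of time are all open, and biomarker comparisons are tested at two-sided 0.05 without multiplicity adjustment. Time needs particular care, because spread is only known at month 6. A simple comparison of MFS by spread could count a man as a spread responder on serum taken after his metastasis.

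**Working it through.** **Step 1. Look for the missing analysis.** Every place in Section 13 where spread or MFS is analysed:

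| Part of Section 13 | Explanatory side | Outcome | Spread with MFS? |
|---|---|---|---|
| Study Endpoints, biomarker endpoint 2 | none | new antibodies at 6 months | No |
| Primary endpoint, exploratory Cox model | cohort, Gleason score, PSA doubling time, PSA | MFS | No, spread absent |
| Biomarker endpoints, baseline-response models (logistic and Cox) | baseline immune responses | later Th1-biased responses; 2-year MFS | No, spread is a month-6 change |
| Biomarker endpoints, antigen-spread model (logistic) | arm, 6-month PAP response | spread | No, MFS absent |
| Biomarker endpoints, bone-imaging models | NaF PET/CT measures | progression | No, spread absent |

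Objective 1, on baseline responses, and objective 4, on baseline NaF PET/CT lesions, each have a model that matches their wording. Objective 2 has its own model, but of another question.

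**Step 2. Why a landmark is needed.** Section 8.B takes men off study when metastasis appears. The same section and Sections 10.I and 10.J continue blood draws to 12 months in men already off study. A man with metastasis at month 4 can therefore supply the month-6 serum that classifies him. Conversely, men without a month-6 sample cannot be classified at all, so those classified are partly selected on still being followed. Starting the comparison at month 6, in men then free of metastasis, removes both problems.

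**Step 3. What the added analysis could detect.** The documents give no power for spread, so there is no stated figure to reproduce. Inputs: 50 men in the biomarker cohort (Section 13); two-sided 0.05 (Section 13); 2-year MFS of 40% without spread and 70% with it. The last pair is an assumption, borrowed from the between-arm contrast in the power section. The share of men with spread is also assumed. No attrition is allowed for.

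Power = Φ[(0.30 − 1.96·se0)/se1], where se0 = √[p̄(1−p̄)(1/n0+1/n1)], se1 = √[0.24/n0 + 0.21/n1], and p̄ is the weighted mean MFS.

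For 25 men with and 25 without spread: p̄ = 0.55, se0 = 0.1407, se1 = 0.1342, and (0.30 − 0.2758)/0.1342 = 0.18, so power is 0.57.

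| Share with spread | n without / with | Power |
|---|---|---|
| 20% | 40 / 10 | 0.39 |
| 50% | 25 / 25 | 0.57 |
| 80% | 10 / 40 | 0.42 |
| 90% | 5 / 45 | 0.28 |

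**Step 4. Could noise alone reach one of 126?** Let f be the chance that one antigen is falsely called new. It is not in the documents. With antigens independent, P(at least one) = 1 − (1 − f)^126:

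- f = 0.1% gives 12%
- f = 0.5% gives 47%
- f = 1% gives 72%
- f = 2% gives 92%

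Now put in the assay rules.

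- *Replicate rule alone.* With per-replicate error r, a false call has probability s = 3r²(1−r) + r³, and a false new call s(1−s). The chance of at least one is 4% at r = 1%, 14% at r = 2% and 60% at r = 5%.
- *Reviewer rule added.* With reviewer error v, replace r by 4v³(1−v) + v⁴. With all errors independent, the result is below 0.01% at v = 5%, 0.5% at v = 10% and 24% at v = 20%.

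The answer runs from negligible to most of the cohort, depending on an error rate and an error correlation that the documents do not give.

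**The case against.** The objective is labelled exploratory, concerns 50 men and has no bearing on the primary endpoint or safety. The missing comparison would be underpowered in any case. All of that stands and limits the weight of the point. It does not supply the analysis.

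A reader might go further and infer that the spread variable will saturate on assay noise. The documents do not support this. Section 11.B.5 requires agreement of three of four reviewers and two of three replicates, with ELISA confirmation where feasible, and Step 4 shows that these rules could make noise negligible. They do not settle the matter the other way either. Replicates sit on one membrane and reviewers read the same spots, so their errors may be correlated, and variation between visits is not directly controlled. Saturation remains a conditional risk.

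Three other readings also go too far. Spread is not modelled against PAP response alone, since arm is a covariate and a descriptive summary of the antigens recognised is planned. Counting only gains is not an error, because the objective defines spread as the development of responses. And noise unrelated to arm would usually dilute an association rather than create one, with the GM-CSF-only arm as a concurrent reference.

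**Conclusion.** The mismatch between objective and analysis holds and rests on no assumption: objective 2 names MFS, and no analysis in Section 13 pairs MFS with antigen spread. The effect is that one exploratory objective goes unanswered.

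The power range of 0.28 to 0.57 is illustrative. It depends on the assumed 40% versus 70% MFS, on a spread prevalence between 20% and 90%, and on all 50 men being analysed. It would be lower after landmark exclusions, so a null result should not be read as evidence against an association.

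The noise question supports only a reporting check, because the per-antigen false-new rate is unknown.

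**What to change.** In Section 13, Biomarker endpoints, add after the antigen-spread model: a Cox analysis of MFS (or a logistic analysis of 2-year MFS) by month-6 antigen spread, in men metastasis-free at a month-6 landmark, adjusted for treatment arm and labelled exploratory. State the landmark as a fixed time after the month-6 visit and scan windows close, and count MFS from there.

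As a check on the yes/no variable, report the number of antigens gained from baseline to month 6 beside the number lost, by arm, and name the panel used. Losses may include real waning, so they are a guide to test-retest variation and not a direct measure of it.

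The cost is a few sentences of SAP text, one extra model and one extra table, all from sera and scans already planned. The downside is that men with metastasis by month 6 leave the analysis, which removes events from a comparison that is already small.

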^e This blood draw not required if patient off-study prior to 12 months. However, all subjects should have blood drawn for immune monitoring up to 12 months, at the quarterly intervals (+/- 1 week) even if off-study prior to that time.

^f After the End of Study Visit, subjects will be contacted by telephone annually for up to 2 years to collect clinical information to identify any potential long-term risks. This information has been requested by

FDA for all gene delivery trials to assess potential long-term risks. See section 10.J.1 for additional details.

^g Day 127 (Month 4.5) can be +/- 10 days – blood draw visit only

^h NaF PET/CT within 14 days of study visit

ⁱ Consenting to be performed within 4 months (112 days) of study registration

^j Not required if already performed within 14 days

^k These NaF-PET/CT studies will be performed at UWCCC and JHU clinical sites only

^l Baseline leukapheresis required at UWCCC site only. 200-cc blood draw (heparinized green-top tubes) permitted as an alternative to leukapheresis at JHU and UCSF trial sites, and at 6-month time point for UWCCC.

^mBlood and leukapheresis samples at screening must be collected before tetanus immunization. DNA immunization/GM-CSF must be at least 24 hours after the tetanus immunization.

1. Introduction

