The following section describes the schedule for prescreening, vaccine/GM-CSF inoculations, clinical and laboratory evaluations. When a chemistry panel is indicated the following tests are performed: creatinine, glucose, SGOT, bilirubin, alkaline phosphatase, amylase, and LDH. (Note: serum glucose not required in expanded biomarker cohort). This plan is summarized in the Schema.

A. Prescreen (performed within 4 weeks of study registration unless otherwise noted)

1. Confirm potential eligibility by history, pathology, diagnosis, and serial serum PSA levels; no exclusions by history
2. CT scan of abdomen and pelvis, bone scan
3. Sign consent form (to be done within 4 months prior to study registration)

B. Screening Evaluation (performed within 2 weeks of study Day 1; can coincide with prescreen evaluation)

1. Physical examination, including vital signs, symptoms assessment, and ECOG performance score
2. Evaluation of blood cell counts (CBC with platelets), chemistry panel, serum prostate specific antigen (PSA), serum PAP, serum testosterone.
3. Randomization - treatment arm assignment
4. Tetanus immunization: must be at least 24 hours before initial DNA immunization/GM-CSF treatment, and not to be completed until after blood and leukapheresis samples are collected for baseline immune studies.
5. 20 ml peripheral blood (red-top tubes) for sera to evaluate baseline antibody responses, and 100 ml peripheral blood (green-top heparinized tubes) for T-cell response evaluation. Must be collected prior to tetanus immunization.
6. BIOMARKER COHORT ONLY: Leukapheresis (~1.0 blood volume, 100 mL collection) for baseline T-cell response evaluation (can be performed +/- 7 days of this study visit, and replaces 100-ml peripheral blood requirement in 10.B.5 above). NOTE: This is required at UWCCC site only. As an alternative to leukapheresis, 200 ml peripheral blood (green-top heparinized tubes) can be collected at other clinical sites. This is for pre-treatment T-cell response evaluation and immune biomarker studies and must be collected prior to tetanus immunization.
7. BIOMARKER COHORT ONLY: NaF PET/CT (can be performed +/- 14 days of this screening time point). NOTE: This study is for research purposes only, will not be used to determine eligibility, and will not be used for clinical response evaluation or treatment decisions. This study will only be performed at designated sites (UWCCC and JHU).

C. First immunization/GM-CSF treatment visit (day 1)

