1. Physical examination, including vital signs, symptoms assessment, and ECOG performance score (not required if already obtained within 14 days)
2. Blood draw for serum PSA and PAP (to be obtained prior to administration of immunization/GM-CSF). May be done up to 3 days in advance of Day 1.
3. Immunization as described in sections 6 and 8 above. Specifically, subjects will receive immunizations intradermally on the deltoid area of the lateral arm (preferentially left arm) with 0.25 cc administered at each of two adjacent sites.
4. Following vaccinations, the subjects will be observed for 60 minutes for unanticipated adverse events.

D. Second, third, fifth and sixth biweekly treatment visits (days 15, 29, 57 and 71, each +/- 2 days)

1. Symptoms assessment
2. Immunization/GM-CSF and post-treatment monitoring as described above

E. Fourth immunization/GM-CSF treatment visit (day 43 +/- 2 days)

1. Physical examination, including vital signs, symptoms assessment, and ECOG performance score
2. Blood draw for CBC, chemistry panel, serum PSA and PAP (to be obtained prior to administration of immunization/GM-CSF)
3. Immunization/GM-CSF and post-treatment monitoring as described above

F. End of initial vaccination series evaluation (2 weeks after sixth vaccination, i.e. month 3 (day 85 +/- 2 days)

1. Physical examination, including vital signs, symptoms assessment, and ECOG performance score.
2. Blood draw for CBC, chemistry panel, serum PSA and PAP (to be obtained prior to administration of immunization/GM-CSF)
3. 10 ml peripheral blood (red-top tubes) for sera to evaluate antibody responses, and 100 ml peripheral blood (green-top heparinized tubes) for T-cell response evaluation
4. Immunization/GM-CSF and post-treatment monitoring as described above
5. BIOMARKER COHORT ONLY: NaF PET/CT (can be performed +/- 14 days of this 3-month immunization/GM-CSF visit). NOTE: This study is for research purposes only and will not be used for clinical response evaluation or treatment decisions. This study will be performed only at designated sites (UWCCC and JHU).

G. Day 127 (+/- 10 days) – BIOMARKER COHORT ONLY

1. Blood draw for serum PSA and PAP (does not require a clinic visit; the purpose of this draw is to provide PSA values to determine a PSA doubling time

corresponding with the 3-6 month period over which NaF PET/CT scans are obtained).

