H. Quarterly booster immunizations (every 3 months (days 169, 253, 337, 421, 505, 589, each +/- 7 days) – beginning at month 6 immunization – up to 6 total (to complete 2-year treatment course)

1. Physical examination, including vital signs, symptoms assessment, and ECOG performance score
2. Blood draw for CBC, chemistry panel, serum PSA and PAP (to be obtained prior to administration of immunization/GM-CSF)
3. Immunization/GM-CSF and post-treatment monitoring as described above
4. CT scan abdomen/pelvis and bone scan – performed prior to second quarterly booster/treatment (i.e. 6 months after first immunization/treatment), and every 6 months (every other visit) thereafter. Can be performed +/- 7 days of study visit.
5. 10 ml peripheral blood (red-top tubes) for sera to evaluate antibody responses, and 100 ml peripheral blood (green-top heparinized tubes) for T-cell response evaluation (Quarterly for 1st year following initial series, 3 time points, only)
6. BIOMARKER COHORT ONLY: Leukapheresis (~1.0 blood volume, 100 mL collection) at month 6 evaluation for T-cell response evaluation (can be performed +/- 14 days of this study visit). This leukapheresis replaces 100-ml peripheral blood requirement in 10.G.5 above for the month 6 time point. NOTE: As an alternative to leukapheresis, 200 ml peripheral blood (green-top heparinized tubes) can be collected. This is for T-cell response evaluation and immune biomarker studies.
7. BIOMARKER COHORT ONLY: NaF PET/CT (to be performed +/- 7 days of the 6-month immunization/GM-CSF visit). NOTE: This study is for research purposes only and will not be used for clinical response evaluation or treatment decisions. This study will also be performed only at designated sites (UWCCC and JHU).

I. End of Study Visit or 2-year (Day 672 +/- 7 days) Off-Study Visit

1. Physical examination, including vital signs, symptoms assessment, and ECOG performance score
2. Blood for CBC, chemistry panel, serum PSA, serum PAP
3. 10 ml peripheral blood (red-top tubes) for sera to evaluate antibody responses, and 100 ml peripheral blood (green-top heparinized tubes) for T-cell response evaluation. [Note: these specimens not required if subject off study prior to 12 month visit. However, these will continue to be drawn at quarterly intervals up to 12 months after screening/randomization in all subjects, even if off-study prior to 12 months.]

J. Follow up for Subjects Who Come Off Study Prior to 12-Month Visit

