nomogram(<http://www.mskcc.org/applications/nomograms/prostate/PsaDoublingTime.aspx>). The post-treatment PSA doubling time will be calculated using the same nomogram from:

- (1) All PSA values obtained from the same clinical laboratory using the same PSA assay beginning with the PSA value at day 1 (week 0) and continuing until the end-of study (or month 24) value (PSADT₀₋₂₄).

(2) All PSA values obtained from the same clinical laboratory using the same PSA assay beginning with the PSA value at day 85 (month 3) to the day 253 (month 9) value (PSADT₃₋₉).

An increase in the PSA doubling time to at least double the baseline value, and at least 15 months, will be considered a PSA doubling time “response” [7].

D. Quantitative Total Bone Imaging (QTBI) using NaF PET/CT

An assessment of small volume bone metastatic disease (potentially not detected by standard bone scintigraphy) and tumor growth rates will be conducted using QTBI. Patients accrued to the Biomarker Cohort at designated clinical trial sites will be assessed at baseline, 3 months and 6 months by NaF PET/CT. Metastatic prostate cancer lesions in bone will first be localized and identified based on functional NaF PET uptake, assisted with the anatomical information provided by CT scans. Segmentation will be performed using an automatic segmentation method (e.g. a fixed SUV threshold), and adjusted with physician guidance. Scans from different time points will be registered to one another using an articulated registration technique employing a rigid registration of skeletal elements (bones) from CT followed by registration optimization by combining with deformable registration of bones and lesions from NaF PET/CT. The lesions between pre-treatment and follow-up scans will be matched to establish longitudinal correspondence of the lesions. For each patient, comprehensive treatment response metrics will be calculated, consisting of SUV_{total} (total disease burden), SUV_{max} (maximum intensity lesion), SUV_{mean} (average intensity), the number of lesions, and total volume of bone lesions. In addition, imaging response metrics will be calculated for each individual lesion. This methodology will specifically be used to assess the growth rate of bone metastatic disease by evaluating changes from baseline to month 3 and from month 3 to month 6. In terms of logistics, each of the clinical centers has the capacity and expertise to perform NaF PET imaging.

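### Section 13 should define bone-lesion growth rate by NaF PET/CT as log change per unit of actual time over the two intervals named in Section 11.D, not leave it as unscaled percent change from baseline (exploratory objective 5 only)

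*Combined protocol and SAP*

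**What the plan says.** **Objective.** Section 5.D, objective 5, asks whether lesion growth rates from NaF PET/CT, and shifts in those rates, go with PSA doubling time and its changes.

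**Method section.** Section 11.D says that growth rate will be assessed "by evaluating changes from baseline to month 3 and from month 3 to month 6". It also describes the first scan as pre-treatment.

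**Analysis section.** Section 13 (Biomarker endpoints, analysis) says that percent "changes in QTBI parameters from the baseline to the 3 and 6 months assessment will be calculated" and summarized by arm with the usual descriptive statistics. The next sentence gives a linear mixed model with subject random effects, which "will be used to evaluate the association between changes in QTBI parameters and changes in PSA doubling time". Neither sentence mentions scan dates, elapsed time or the month 3 to month 6 interval.

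**Scan windows.**
- Baseline, Section 10.B.7: "NaF PET/CT (can be performed +/- 14 days of this screening time point"; screening itself is within 2 weeks of Day 1.
- Month 3, Section 10.F.5: "can be performed +/- 14 days of this 3-month immunization/GM-CSF visit"; the visit is Day 85 +/- 2 days.
- Month 6, Section 10.H.7: "NaF PET/CT (to be performed +/- 7 days of the 6-month immunization/GM-CSF visit"; the visit is Day 169 +/- 7 days.
- Biomarker cohort schedule, footnote h, attached to both follow-up scans: "NaF PET/CT within 14 days of study visit".

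**The concern.** A growth rate is a change per unit of time. A percent change between two scans depends on both the growth rate and the days between the scans, so if the days vary between men, scan dates add noise. Objective 5 relates the imaging measure to PSA doubling time, which is already on a time scale. Noise from scan dates would blur that association, in a cohort of at most 50 men scanned at two sites.

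The two percent changes in Section 13 also share the baseline scan and overlap in time. Objective 5 needs two successive rates and the difference between them, and Section 13 states neither the second rate nor the difference. Section 10.G shows that the later interval was meant to matter: the Day 127 PSA draw is there to give a doubling time for the months between the second and third scans.

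Finally, the baseline window, read literally, allows a scan after the first dose. Such a scan would not be a pre-treatment value for the growth analysis, nor for the Cox and logistic analyses of baseline lesions.

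**Working it through.** The documents give no figure for the scan interval, so there is none to reproduce. The check is arithmetic on the stated windows. Days are numbered consecutively with Day 1 as the first dose.

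**Step 1. Permitted scan days**
- Screening: 1 - 14 = Day -13 at the earliest, Day 1 at the latest.
- Baseline scan: -13 - 14 = Day -27 to 1 + 14 = Day 15.
- Month 3 scan: 85 - 2 - 14 = Day 69 to 85 + 2 + 14 = Day 101.
- Month 6 scan under 10.H.7: 169 - 7 - 7 = Day 155 to 169 + 7 + 7 = Day 183.
- Month 6 scan under footnote h: 169 - 7 - 14 = Day 148 to 169 + 7 + 14 = Day 190.

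**Step 2. Permitted intervals**

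Shortest = earliest later scan minus latest earlier scan. Longest = latest later scan minus earliest earlier scan.

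| Interval | Reading | Shortest | Longest | Ratio |
|---|---|---|---|---|
| Baseline to month 3 | windows as written | 69 - 15 = 54 | 101 + 27 = 128 | 2.37 |
| Baseline to month 3 | baseline scan by Day 1 | 69 - 1 = 68 | 128 | 1.88 |
| Baseline to month 6 | 10.H.7 | 155 - 15 = 140 | 183 + 27 = 210 | 1.50 |
| Baseline to month 6 | footnote h | 148 - 15 = 133 | 190 + 27 = 217 | 1.63 |
| Month 3 to month 6 | 10.H.7 | 155 - 101 = 54 | 183 - 69 = 114 | 2.11 |
| Month 3 to month 6 | footnote h | 148 - 101 = 47 | 190 - 69 = 121 | 2.57 |

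If screening is at latest the day before Day 1, the first row becomes 55 to 128 days (2.33-fold). A baseline scan by Day 1 narrows the baseline intervals but leaves month 3 to month 6 unchanged.

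**Step 3. Effect on the reported value**

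Assume exponential growth with doubling time T, which the documents do not give. Percent change over d days = 100 x (2^(d/T) - 1).

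| T (days, assumed) | d = 54 | d = 68 | d = 128 |
|---|---|---|---|
| 90 | 52% | 69% | 168% |
| 180 | 23% | 30% | 64% |
| 365 | 11% | 14% | 28% |

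An apparent change in growth can also arise where there is none. Take T = 180 and scans on Days 1, 69 and 183, so the baseline scan is not late. The first interval is 68 days and reads +30%. The second is 114 days and reads 100 x (2^(114/180) - 1) = +55%. The growth rate is identical in both.

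**Step 4. Which scaling removes the effect**

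Dividing percent change by time is not enough. With T = 91, percent change per 30 days is (2^(55/91) - 1) x 100 x 30/55 = 28% at 55 days and (2^(128/91) - 1) x 100 x 30/128 = 39% at 128 days. The log change per day is ln(2)/T at every d. With T = 180, ln(1.231)/54 and ln(1.637)/128 are both 0.00385 per day.

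**The case against.** Several readings stronger than the one made here are tempting, and the documents do not support them.

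- *The month 3 to month 6 change is not analysed.* Section 11.D says that it will be evaluated, and this is one combined protocol and SAP. With a non-zero baseline it can also be recovered as (1 + p6)/(1 + p3) - 1 from the proportional changes to months 3 and 6. What stands is that Section 13 does not specify it.
- *Raw percent changes go into the mixed model.* The percent changes are specified as descriptive summaries, and the model sentence does not say what its inputs are. The fair criticism is that they are undefined.
- *Every interval varies more than two-fold.* Baseline to month 6 varies 1.5- to 1.6-fold. Baseline to month 3 exceeds two-fold only if a post-dose baseline scan is allowed.
- *Baseline scans will follow dosing.* The wording of 10.B.7 permits it, but 11.D calls the scan pre-treatment and the schedule places it in the screening column. This is a loophole in the wording, not a stated intention.

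The ranges are also extremes, with every window at its limit; typical spread will be smaller. Because the trial is randomized and blinded, scan timing should mostly add noise rather than favour an arm. Section 11.D refers to an imaging SOP that is not in these documents, so time scaling may be described there. These points limit the size of the problem. They do not supply the missing definition, which belongs in the analysis section.

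**Conclusion.** The point holds as a cheap improvement to one exploratory objective. Section 13 does not define a growth rate or a change in growth rate, although objective 5 is about both and Section 11.D names the intervals. At the permitted extremes, the interval varies 1.9- to 2.4-fold for baseline to month 3, 1.5- to 1.6-fold for baseline to month 6, and 2.1- to 2.6-fold for month 3 to month 6. The effect on the reported percentages rests on assumed exponential growth and assumed doubling times of 90 to 365 days, and no realistic loss in the strength of the association has been estimated.

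Two pairs of passages conflict and must be reconciled: 10.B.7 with the pre-treatment scan in 11.D, and 10.H.7 with footnote h for month 6. A reader might infer a threat to the main result. There is none: Sections 7.B.9 and 8.B exclude NaF PET/CT from eligibility and from the definition of progression.

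**What to change.** In Section 13:
1. Define growth rate as [ln(later value) - ln(earlier value)] divided by the days between the two actual scan dates, separately for baseline to month 3 and month 3 to month 6.
2. Define change in growth rate as the second rate minus the first.
3. Name these as the QTBI inputs to the mixed model. The percent changes can stay as descriptive summaries.
4. State a rule for zero values. Men enter without bone-scan metastases, so some may have no measurable lesion. Percent change from a zero baseline is undefined too, so the present text needs such a rule as well.

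In the protocol, reconcile the 10.B.7 window with the pre-treatment description in 11.D, and give one month 6 scan window in 10.H.7 and footnote h. The choice of window is for the sponsor.

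The cost is SAP wording, a short protocol clarification and a little more analysis work. No extra scans are needed, on the assumption that scan dates are captured. Booking of the baseline scan may become slightly tighter, depending on how the passages are reconciled. The definitions should be fixed before unblinding.
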